Posttest Inquiry. All participants will be administered the MMPI-2-RF-EX Posttest Inquiry (PTI) that has been administered in previous MMPI simulation studies (Creighton et al., 2017), based on recommendations by Rogers (2008). The PTI assesses participants' compliance with condition-specific instructions for completing the MMPI and was adapted for the proposed research. Responses to three questions from this survey ("What instructions did you receive for completing the research study"; "I tried to answer the questions so I would look like I am not suicidal?"; "I tried to appear as suicidal as I could when I took the test") will be examined to assess compliance with instructions. Simulators answering "To fake not having thoughts of suicide" to the first question will be classified as Simulation- Compliant. Alternatively, Simulators answering at least "most of the time" to the second item and "not at all" to the third item will be classified as Simulation-Noncompliant and excluded from analyses. Veterans in the Standard Instructions condition who comply with instructions (e.g., do not produce profiles indicative of content-based invalid responding) are classified as Standard - Compliant while those who do not will be classified as Standard - Noncompliant and excluded from analyses.

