MMPI Condition 2 (Simulated Underreporting): “We want you to imagine that you are undergoing testing as part of standard intake procedures for receiving services in a mental health clinic, which involves completing some questionnaires and a personality test before the first session. You have recently had recurring thoughts of suicide and have thought of ways to attempt suicide. However, you are concerned that you will be hospitalized if you disclose this during testing and do not want to be hospitalized. Please answer the questionnaires as though you are trying to hide or downplay any thoughts of suicide or intent to make a suicide attempt. The questionnaire has some “lie” scales built into it, so try to avoid being detected. If you are able to avoid detection, you will receive an additional \$20 gift card. Additionally, as part of the intake process, you agreed to identify questions that you think are assessing your current risk of suicide. You will use a computer to mark these while taking the questionnaires.”

3.6. Additional incentives following completion of the first portion of the study.

Following the study session, all participants will receive payment in the form of \$50 for participation. Additional incentives are condition-dependent, will be described to participants at the beginning of the study as part of the informed consent process, and administered no later than two weeks following completion of the study protocol:

Simulated Underreporting: Additional payment for undetected underreporting on MMPI-2-RF-EX. Individuals in the Simulated Underreporting condition who do not produce clinically significant MMPI-2-RF-EX K or L scale elevations and are classified as Simulation Compliant based on Posttest Inquiry responses will receive an additional electronic \$20 gift card through email, following recommendations and procedures outlined in previous research (Brown & Sellbom, 2020; Crighton et al., 2017).

3.4. Detailed Study Procedures. One hundred and fifty adult military Veteran participants residing in the United States will complete eight study components during the baseline study session:

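### The Posttest Inquiry rule labels simulators who followed instructions as Noncompliant, conflicts with the sentence before it, and excludes none of those who report not following instructions

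*Combined protocol and SAP*

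**What the plan says.** Section 3.3, Posttest Inquiry, describes the inquiry as a check of "compliance with condition-specific instructions for completing the MMPI and was adapted for the proposed research". Three questions are used. Item 1 asks which instructions were received. Item 2 reads "I tried to answer the questions so I would look like I am not suicidal". Item 3 reads "I tried to appear as suicidal as I could when I took the test".

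Two sentences then classify the simulators:

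- "Simulators answering 'To fake not having thoughts of suicide' to the first question will be classified as" Simulation-Compliant. Items 2 and 3 play no part.
- Those giving at least "most of the time' to the second item and 'not at all' to the third item will be classified as Simulation-Noncompliant", and they are excluded from the analyses. Item 1 plays no part.

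Only the word 'Alternatively' links the two sentences.

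The instruction being checked is in Section 3.5, MMPI Condition 2: "Please answer the questionnaires as though you are trying to hide or downplay any thoughts of suicide or intent to make a suicide attempt". Section 3.6 uses the label a second time. Simulators without clinically significant K or L elevations who "are classified as Simulation Compliant based on Posttest Inquiry responses will receive an additional electronic" $20 gift card, and the condition-dependent incentives "will be described to participants at the beginning of the study as part of the informed consent process". Section 3.8.1, which sets out the MANOVA and the two hierarchical regressions, adds no classification rule.

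**The concern.** The answer pattern that triggers exclusion is the one an obedient simulator would give: tried mostly to look not suicidal, and did not try at all to look suicidal. The plan calls that person Noncompliant and removes them. If the same person also recalls the instruction correctly on item 1, the preceding sentence calls them Compliant, and nothing says which sentence prevails.

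The rule decides who makes up the Simulated Underreporting arm for H1 to H3, all of which contrast that arm with Standard Instructions. A check that can remove only people who enacted the manipulation, and never those who report failing to, tends to dilute the contrast it is meant to protect. It also leaves bonus eligibility undefined for the fully adherent simulator. If the choice of reading is left until the data are in, exclusion becomes a post hoc decision.

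**Working it through.** **1. Set the rules against the instruction.** Condition 2 asks for hiding or downplaying. Endorsing item 2 reports doing so, and answering 'not at all' to item 3 reports not doing the opposite. Together these two answers are the adherent pattern, and they are the conditions of the exclusion sentence.

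**2. Enumerate.** Each item is split in two: item 1 correct or other; item 2 at least 'most of the time' or less; item 3 'not at all' or some. That gives 2 × 2 × 2 = 8 combinations.

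| Item 1 | Item 2 | Item 3 | Label as written |
|---|---|---|---|
| correct | at least most | not at all | Compliant and Noncompliant (excluded) |
| correct | at least most | some | Compliant |
| correct | less | not at all | Compliant |
| correct | less | some | Compliant |
| other | at least most | not at all | Noncompliant (excluded) |
| other | at least most | some | none |
| other | less | not at all | none |
| other | less | some | none |

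The totals are 3 Compliant only, 1 both, 1 Noncompliant only and 3 unlabelled. The exclusion sentence catches 2 combinations, both with the adherent item 2/3 pattern. None of the other 6 is excluded, and these include all 4 with item 2 below 'most of the time'. The counts show logical coverage. They do not say how many participants fall in each cell.

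**3. The plan's own power figure, for context.** Section 3.2 gives .98–.99 (printed as β) for medium effects in regression with 150 participants. Taking f² = 0.15 and α = 0.05 (both assumed; the plan states neither), the noncentrality is f² × N = 0.15 × 150 = 22.5. Power is then 0.992 with two predictors and 0.985 with three, which agrees. The finding does not depend on this figure.

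**4. Illustrative size.** The inputs are 75 per arm (Section 3.2), an assumed d = 0.5, and a two-sided α of 0.05. A two-sample t-test stands in for the planned MANOVA and regressions. Its noncentrality is d × √(n₁n₂/(n₁+n₂)) on n₁+n₂−2 degrees of freedom.

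- *Exclusion sentence governs; 80–95% show the adherent item 2/3 pattern (assumed).* Retained: 75 × 0.20 = 15 down to 75 × 0.05 = 3.75, about 4. For 15 vs 75, noncentrality is 0.5 × √(1125/90) = 1.77 and power 0.416. For 4 vs 75, it is 0.5 × √(300/79) = 0.97 and power 0.161.
- *Item 1 governs; 80–95% answer it correctly (assumed).* Retained: at least 75 × 0.80 = 60 to 75 × 0.95 = 71.25, about 71. The number is higher if some who miss item 1 also lack the item 2/3 pattern, because no sentence excludes them. For 60 vs 75, noncentrality is 0.5 × √(4500/135) = 2.89 and power 0.818. For 71 vs 75, it is 0.5 × √(5325/146) = 3.02 and power 0.851.
- *Reference, 75 vs 75.* Noncentrality is 0.5 × √37.5 = 3.06 and power 0.860.

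The 0.16–0.42 range is optimistic. It credits the retained simulators with the full effect, although they are the ones whose answers depart from the instructed pattern.

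**The case against.** The strongest reply is that this is an obvious drafting slip. An analyst about to discard 80–95% of an arm for doing as told would notice at once. On the milder reading, where item 1 governs, the illustrative loss is only 1 to 4 points of power. A slip is indeed likely, and the severe scenario would be conspicuous. But spotting the slip does not reveal the intended rule. 'Noncompliant' may stand for 'Compliant', although the same sentence also says 'excluded'. A 'not' may be missing, the anchors for items 2 and 3 may be swapped, or the sentence may have been meant for the Standard arm. These give different analysis sets. Under all of them the adherent pattern must stop being excluded.

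A second reply is that simulators who miss item 1 are implicitly not Compliant and would be dropped. That is a reasonable inference, but no sentence says it. It would still keep someone who recalls the instruction and reports not following it.

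It is also fair to say that the adherence shares and d = 0.5 appear nowhere in the documents. The contradiction stands without them. The consent pages are not available here, so no inconsistency in them is alleged.

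**Conclusion.** The concern holds, and the rule must be fixed before analysis. As written, the two simulator sentences contradict each other for the fully adherent participant, leave 3 of 8 combinations unlabelled, and exclude only combinations with the instructed item 2/3 pattern. This conclusion rests on the text alone.

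The practical size depends on which sentence is coded as governing: large if the exclusion sentence is applied, small if item 1 is. The power ranges are illustrations under assumed adherence and effect size. The roughly 15% allowance in Section 3.2 is for non-content-based invalid responding and does not cover this exclusion.

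**What to change.** Before analysis:

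1. Reverse the exclusion, so that item 2 at least 'most of the time' together with item 3 'not at all' counts toward Simulation-Compliant.
2. State one rule that assigns every one of the 8 combinations. The sponsor should confirm whether Compliant means item 1 AND the item 2/3 pattern (1 of 8 combinations) or item 1 OR that pattern (5 of 8). If item 1 alone was intended (4 of 8), the text should say so and acknowledge that 3 of those 4 combinations report departing from the instruction.
3. State that all other simulators are Simulation-Noncompliant and excluded.
4. Use the same definition for the bonus in Section 3.6, and check that the consent wording agrees with it.
5. Report an all-randomised sensitivity analysis alongside. The contradiction can be cured without it, but it shows how far the results depend on exclusions made after randomisation.

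The cost is one or two sentences in Section 3.3, a matching definition in Section 3.6 and a check of the consent text. No extra participants, data or procedures are needed, and the sensitivity analysis uses data already collected.

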Military veterans comprise 7.9% of the US population but account for 13.5% of adult deaths by suicide; additionally, the Veteran suicide rate is 1.5 greater than that of the general population (US Department of Veterans Affairs, 2019). A disproportionate number of suicides are attributed to Veterans who have not recently received healthcare within the Veterans Affairs (VA) Healthcare System. Indeed, the age- and sex-adjusted suicide rates among these Veterans increased by 11.8% between 2016 and 2017, compared to an increase of 1.3% among Veterans recently utilizing VA health care services, highlighting the increasing pace of suicide rates among Veterans not receiving health care within VA, a group which constitutes the majority of Veterans (US Department of Veterans Affairs, 2019). Given the heightened suicide rate among this group of Veterans, implementation of empirically-based suicide assessment procedures would be well-served in other Veteran-serving community settings. However, research and clinical efforts to identify Veterans at highest risk of suicide have been met with limited success (Nelson et al., 2017). Further complicating suicide risk assessment in the Veteran population is the tendency for high risk populations to not disclose current levels of suicide risk (Anestis & Green, 2015). **Therefore, it is critical that empirically-derived methods of assessing suicide risk accurately identify Veterans outside the VA setting who are at risk of suicide, but do not accurately report their current experiences of suicidal ideation or intent.** However, current measures of suicide risk commonly administered in research and clinical settings are not well-suited to accomplish this task. **The proposed study is well-suited to address these limitations and expand upon preliminary findings in Veteran samples through two of its aims: 1) examine whether simulated underreporting on the MMPI-2-RF-EX (indexed by K and L scores) impacts SUI scores and generalizes to underreporting on extratest self-report measures of suicide risk and 2) assess the incremental predictive utility of MMPI-2-RF-EX L and K scales in differentiating between these groups.**

In response to enhanced detection of suicide risk, there is a need to identify psychotherapeutic interventions targeting suicide risk among military veterans who may be unable or unwilling to seek

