2.1.2 The MMPI in detecting underreporting and its extension to extratest measures

A growing body of evidence indicates that underreporting on the MMPI instruments generalizes to conjointly administered self-report measures. Forbey and Lee (2011) observed that individuals who produced significantly elevated MMPI-2 K and L scale scores endorsed significantly lower mean scores on several conjointly administered self-report measures assessing various symptoms of psychopathology with roughly medium to large sized effects. Additionally, Forbey and colleagues (2013) observed that scores on internalizing self-report measures, namely the Beck Depression Inventory (Beck, Ward, Mendelson, Mock, & Erbaugh, 1961), were also significantly lower for the content-based underreporting group with medium to large effects. Indeed, individuals indicated as underreporting on the MMPI-2 and MMPI-2-RF respond in a similar manner to extratest measures of psychopathology in university, VA psychiatric inpatient, and correctional settings (Forbey & Lee, 2011; Forbey et al., 2013).

Underreporting may result in false negative findings, particularly in high-stakes assessments (Crighton, Marek, Dragon, & Ben-Porath, 2017). However, limited quantitative research has focused on identifying underreporting in suicide risk assessment, a limitation noted in the current research base (Burchett and Ben-Porath, 2019). Indeed, preliminary evidence indicates that underreporting on the MMPI-2 may have implications for suicide risk assessment. During clinic intake procedures, individuals who denied current suicide ideation/behavior on both a clinician-administered phone interview and the MMPI-2 produced higher K, S, and ODep scores than those who responded affirmatively to only MMPI-2 questions or both the interview and MMPI-2 items (Glassmire, Stolberg, Greene, & Bongar, 2001). However, no research has extended this research to Veterans outside of the VA setting or examined whether the MMPI-2-RF-EX possesses similar clinical utility of previous iterations of the MMPI to accurately identify Veterans who underreport current suicide risk.

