Divergent findings regarding differences in SUI scores between those classified as underreporting and those producing scores within normal limits on content-based validity scale scores support the further clinical need for examining the impact of MMPI-indexed underreporting on suicide-related criterion, including those embedded into the MMPI. While no significant mean differences in MMPI-2-RF SUI scores between these two groups have been observed (Crighton et al., 2017), including in Veteran samples (Forbey et al., 2013; Khazem et al., In Press), significant differences with small-sized effects have also been observed in other samples (Brown & Sellbom, 2020; Khazem et al., In Preparation). Further, as these studies were not aimed at identifying patterns of responding for individuals attempting to conceal suicidal ideation or intent, it is unclear how these individuals, particularly within the Veteran population, would respond to SUI items - and extratest measures of suicide risk and psychopathology. Research employing a simulated groups design in Veteran-serving clinics unaffiliated with VA is well-suited to address these limitations and expand upon previous findings.

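### Standard-arm participants can be excluded after randomisation for a content-based invalid MMPI profile, a rule not stated for simulators; read as L/K, it selects on the H1 outcomes in one arm only

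*Combined protocol and SAP*

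**What the plan says.** Participants are randomised before they take the MMPI-2-RF-EX (Section 3.5), so any exclusion based on the test comes after randomisation.

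- **Standard arm.** Section 3.3 (Posttest Inquiry) keeps those who "comply with instructions (e.g., do not produce profiles indicative of content-based invalid responding) are classified as Standard - Compliant" and excludes the rest. The profile criterion follows an e.g. and is the only one given.
- **Simulated arm.** The same paragraph classifies simulators by their answers to Posttest Inquiry items. No profile criterion is stated. Under Section 3.6 the extra gift card goes to simulators "who do not produce clinically significant MMPI-2-RF-EX K or L scale elevations and are classified as Simulation Compliant based on Posttest Inquiry responses", so an elevation affects payment and no exclusion is attached to it.
- **The Inquiry itself.** It is given to everyone, and three answers "will be examined to assess compliance with instructions", but no answer-based rule is written for the Standard arm.
- **Meaning of content-based.** The plan does not define the term. Section 2.1.2 uses it for underreporting: scores on internalizing measures "were also significantly lower for the content-based underreporting group with medium to large effects", and a contrast is drawn between "those classified as underreporting and those producing scores within normal limits on content-based validity scale scores". The same section describes underreporting through people with raised K and L ("individuals who produced significantly elevated MMPI-2 K and L scale scores endorsed significantly lower mean scores on several conjointly administered self-report measures"), and Section 2 refers to "simulated underreporting on the MMPI-2-RF-EX (indexed by K and L scores").
- **Role of L and K.** They are the H1 outcomes and the H3 predictors (Section 1). Section 3.8.1 enters them in a seven-outcome MANOVA and in the hierarchical regressions. It plans no analysis of all randomised participants.

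**The concern.** H1 asks whether L and K are higher under the underreporting instruction. If the Standard arm is first stripped of members with high L or K while the Simulated arm is left alone, the Standard means fall by construction. The arms then differ even when the instructions have no effect, and randomisation no longer protects the comparison. The Standard-arm spread shrinks too, which enlarges standardised effects. H3 uses the same two scales as predictors, and H2 can be affected to the extent that L and K correlate with the suicide measures.

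The undefined term is a second problem. With no scale or cut-off named, the choice could be made after the data are seen.

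**Working it through.** **The plan's own figure.** The only nearby number is the regression power of .98-.99 in Section 3.2. It reproduces with an assumed f² = 0.15 and alpha 0.05: 0.992 (two predictors) and 0.997 (one-predictor increment) at N = 150, and 0.978 and 0.991 after the 15% loss (N about 127). It does not bear on this point. The 15% allowance is for non-content-based responding only, and sample size does not remove bias.

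**Inputs.** From the documents: 75 per arm and seven MANOVA outcomes (L, K, SUI, BSS, SCS, PCL-5, Short Grit Scale). Assumed, because the documents give none: normal T-scores with SD 10, mean T50 (or T45), L-K correlation 0.4, L/K with the other five outcomes -0.3, 0.5 among those five, cuts at T60, T65 and T70, two-sided 5% tests. Both arms have identical distributions, so every difference is spurious.

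**Reading 1: L/K only.** A Standard participant is kept if L and K are both below the cut. Let c = (cut - mean)/SD, ρ = 0.4 and P = Pr(L < c and K < c). The fall in the Standard mean on L, in SD units, is

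(1 + ρ) × φ(c) × Φ(c(1 - ρ)/√(1 - ρ²)) / P

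- T60 (c = 1): 1.4 × 0.2420 × 0.7437 / 0.736 = 0.342
- T65 (c = 1.5): 1.4 × 0.1295 × 0.8369 / 0.881 = 0.172
- T70 (c = 2): 1.4 × 0.0540 × 0.9048 / 0.957 = 0.071

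Of 75 Standard participants, about 55, 66 and 72 remain (75 × P). Null simulation with the Simulated arm untouched gives, at mean T50:

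| | No exclusion | T60 | T65 | T70 |
|---|---|---|---|---|
| Standard arm excluded | 0% | 26% | 12% | 4% |
| Spurious d on L | 0 | 0.37 | 0.18 | 0.07-0.08 |
| MANOVA rejects (nominal 5%) | 5.5% | 38% | 12% | 6% |
| L falsely higher (nominal 2.5%) | 2.6% | 54% | 18% | 6% |
| L and K both falsely higher | 0.3% | 35% | 6% | 1% |
| SUI falsely lower (nominal 2.5%) | 2.4% | 12.5% | 6.6% | 3.6% |
| Both H3 increments | 0.0% | 4% | 0.5% | 0.1% |

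Rates for L and for L with K rest on 20,000 trials (standard error at most 0.4 points); the other rates and d rest on 3,000 (at most 0.9 points). d exceeds the mean shift because truncation also reduces the SD.

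**Sensitivity.** A mean of T45 moves every cut half an SD further out, so T60 then behaves like T65 at mean T50: L falsely higher 18% / 7% / 3%, and MANOVA roughly 12% / 6% / 5%. With L-K correlation from 0.2 to 0.6 at mean T50, L is falsely higher in 48-58% / 16-20% / 6-7% of trials and both scales in 26-43% / 4-9% / 1-2%.

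**Reading 2: over-reporting scales as well.** The Standard arm is told to answer honestly (Section 3.5), and one Inquiry item reads "I tried to appear as suicidal as I could when I took the test", so this reading is open. Assume an over-reporting scale correlated -0.4 with L and K, with its top 7% or 16% also removed:

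| d on L | T60 | T65 | T70 |
|---|---|---|---|
| Mean T50, top 7% / 16% | +0.32 / +0.27 | +0.13 / +0.08 | +0.02 / -0.04 |
| Mean T45, top 7% / 16% | +0.12 / +0.08 | +0.02 / -0.04 | -0.04 / -0.10 |

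The shift on L cancels when about the top 31% (mean T50, T65), 10% (mean T50, T70) or 3% (mean T45, T70) are also removed. At mean T50 and T60 it does not cancel at any share below 70%.

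**The case against.** The strongest reply is that the rule is under-specified, and that the bias is conditional on a reading. The profile criterion comes after an e.g., no scale is named, and the uses of content-based in Section 2.1.2 describe earlier studies and do not define this rule. The Inquiry goes to everyone, so answer-based assessment of the Standard arm seems intended. The largest figures need a T60 cut at mean T50, whereas Section 3.6 speaks only of clinically significant elevations. A sample selected for recent ideation may well have lower K. The planned test is a MANOVA, and at strict cuts it is close to its nominal level. Finally, the design wants an honestly responding comparator, so naming scales and cut-offs and adding a sensitivity analysis might be enough.

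Much of this stands as a limit on size. The T60 results are the extreme of the range, the effect is minor at strict cuts, and direction is fixed only on the L/K reading. It does not remove the defect. Under either reading a test-profile exclusion is stated for one arm and not for the other. The plan's own usage points to L and K, and no strict cut can be assumed where none is written. Naming a cut-off on L or K would make the selection reproducible but would leave it in place. An honest comparator can be sought through the Inquiry without using the outcome scales.

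**Conclusion.** The concern holds. As written, the compliance rule allows a one-arm, post-randomisation exclusion on the MMPI profile. Read as L/K, which is how the plan uses the term, it selects on the H1 outcomes and favours H1 without any instruction effect.

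The size cannot be determined from the documents. Under the stated assumptions the false MANOVA rate at mean T50 runs from 6% (T70) to 38% (T60), and at mean T45 from about 5% to about 12%. H3 as worded, which needs both increments, is barely affected at T65 or above. Any effect on H2 depends on the assumed correlations. If over-reporting scales are included, the shift on L can shrink, cancel or reverse.

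No net direction is claimed over all exclusions. The Simulation-Noncompliant definition in Section 3.3 describes behaviour that simulators were told to show, and that wording has its own unresolved effect on the other arm.

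**What to change.** Amend Section 3.3 (Posttest Inquiry) and Section 3.8.1 before analysis:

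1. State that no participant in either arm is excluded on L, K or any other content-based validity scale.
2. Define compliance in both arms from Posttest Inquiry answers only, and write the missing answer-based rule for the Standard arm.
3. Apply any non-content-based invalidity screen identically in both arms.
4. Report H1-H3 in all randomised participants with usable MMPI data beside the compliance-restricted set. Which of the two is primary is the sponsor's choice, stated before analysis.
5. Report the number of exclusions and the reasons by arm.
6. Reconcile the Simulation-Noncompliant wording with the Simulated Underreporting instructions before it is used.

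The cost is wording plus one companion table. No new measure is needed, since every participant already completes the Inquiry. The downside is that Standard-arm L and K means and spread may be somewhat higher and the reported effects less favourable.
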